13.8 Handling of dropouts or missing data

Missing binary efficacy variables will be imputed using nonresponder imputation (NRI). In NRI, each subject with missing data or who has prematurely finished the study will be counted as a nonresponder.

For missing continuous efficacy variables, a multiple imputation (MI) approach will be used. In MI, the missing value is replaced by a set of plausible values, where each value is a Bayesian draw from the conditional distribution of the missing data given the observed data.

Non-monotone missing data (ie, intermittent missing data) will be imputed several times with the Markov Chain Monte Carlo (MCMC) method and monotone missing data will be imputed using a monotone regression model. Each set of imputed data will then be summarized and the summaries will be combined into a single inference (Carpenter and Kenward, 2013).

Safety data will not be imputed.

As a sensitivity analysis, the ACR, PASI, LDI, MASES, and MDA efficacy variables will be analyzed based on observed data in addition to a sensitivity analysis based on multiple imputation of ACR component scores and PASI scores for the ACR and PASI response variables, respectively. Subjects with missing data or who have prematurely finished the study will be treated as missing.

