Descriptive statistics will be displayed to provide an overview of the study results. For categorical variables, the number and percentage of subjects in each category will be presented. The denominator for percentages will be based on the number of subjects included in the respective analysis set. For observed case (OC) summaries, or summaries of data where no imputation is made for missing data, subjects with missing data will be accounted for by including a “Missing” category (corresponding to subjects with missing data for the variable being summarized) as the last row in the list of categories being summarized. Percentages will be presented to 1 decimal place. If the percentage is 100%, no decimal will be presented. If the percentage is 0, no percentage will be presented. The % sign will be presented in the column header, but not with each individual value.

For continuous variables, descriptive statistics will include number of subjects with available measurements (n), mean, standard deviation (SD), median, minimum, and maximum. Decimal places for descriptive statistics will apply the following rules:

- “n” will be an integer.
- Arithmetic and geometric mean, SD, and median will use 1 additional decimal place compared to the original data.

- Coefficient of variation (CV [%]) will be presented with 1 decimal place.
- Minimum and maximum will have the same number of decimal places as the original value.

The number of decimal places used for derived efficacy variables is shown in [Table 3-1](#).

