### 4.2 Handling of missing data

#### 4.2.1 Handling of missing data for efficacy analysis

Calculation of derived efficacy variables in the presence of missing data is described in individual subsections of [Section 8.1](#). All derived efficacy variables will be calculated using observed data, and any resulting missing data will be handled as described in this section. All nonresponder imputation (NRI) and MI imputation as described below will be performed only for subjects in the FAS for PA0009.

Additional methods for deriving the PASI response in the presence of missing data are described in [Section 4.2.2](#).

For assessments missing during PA0008, which were to be used in PA0009 for reporting maintenance of response, the following approach will be used:

- For summaries of binary data following NRI, the imputed value from the PA0008 database will be used.
- For summaries of non-imputed (OC) data, the assessment will be left as missing.

For all visits in PA0009 (including PA0009 EV), missing values for binary secondary/other efficacy variables (ACR20, ACR50, ACR70, PASI75, PASI90, PASI100, MDA) or values, which cannot be constructed (eg, for ACR either tender joint count [TJC]/swollen joint count [SJC] are missing or >2 out of the 5 remaining core set measures are missing) will be imputed using NRI. For each visit, subjects with missing data or who have dropped out of the study will be counted as nonresponders. This includes any subjects with missing Baseline values. For PASI response, NRI will be implemented only for subjects with BSA  $\geq 3\%$  at PA0008 Baseline.

For missing continuous secondary/other efficacy variables an MI approach will be used. This will be performed for the following endpoints:

- TJC and SJC

- Psoriasis Area and Severity Index (PASI)
  - For PASI the MI model will be restricted to subjects with a BSA affected by psoriasis of  $\geq 3\%$  at PA0008 Baseline. Subjects with a BSA affected by psoriasis of  $< 3\%$  at PA0008 Baseline will be excluded prior to performing the procedure outlined below.
- Patient's Global Assessment of Disease Activity (PGADA)
- Physician's Global Assessment of Disease Activity (PhGADA)
- Patient's Assessments of Arthritis Pain (PtAAP)
- Health Assessment Questionnaire – Disability Index (HAQ-DI)
- CRP

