## 8 EFFICACY ANALYSES

Missing efficacy data will be imputed as described in [Section 4.2.1](#) prior to reporting. As a sensitivity analysis, summaries will be repeated based on non-imputed (OC) data for the following variables:

- ACR20, ACR50 and ACR70 response relative to PA0008 Baseline at each visit in PA0009.
- PASI75, PASI90 and PASI100 response relative to PA0008 Baseline at each visit in PA0009.
- MDA at each visit in PA0009.
- Change from PA0008 Baseline in MASES at each visit in PA0009.
- Change from PA0008 Baseline in LDI at each visit in PA0009.

A further sensitivity analysis will be performed for ACR20, ACR50 and ACR70, PASI75, PASI90 and PASI100 responses relative to PA0008 Baseline at each visit. The response endpoint will be re-derived and summarized based on the mean value (across multiple imputations) of the ACR component scores or PASI total score after imputation for missing data.

Efficacy variables will be summarized and listed (including individual raw data and derived domain and total scores, where applicable) for the FAS. Summaries of MASES will be restricted to subjects with a MASES  $>0$  at PA0008 Baseline, of LDI will be restricted to subjects with a LDI  $>0$  at PA0008 Baseline, and of PASI responses will be restricted to subjects with a BSA affected by psoriasis of  $\geq 3\%$  at PA0008 Baseline. Maintenance of response summaries will be restricted to subjects with a response at PA0008 Week 12 for the specific endpoint (where response at PA0008 Week 12 is taken directly from the PA0008 datasets).

Responder variables (eg, ACR20 response) will be derived relative to the PA0008 Baseline and summarized using n and percentage at each visit, by treatment group at completion of PA0008 and overall.

Maintenance of response will be assessed for ACR20, ACR50, ACR70, PASI75, PASI90 and PASI100. The responses will be derived relative to PA0008 Baseline and summarized using n and percentage at each post-PA0008 Baseline visit, by treatment sequence across PA0008 and PA0009. These summaries will therefore include PA0008 Week 2, 4, 8, 12, 16 (for ACR only), 20 (for ACR only), 24, and 36 and PA0009 EV [PA0008 Week 48], Week 12, 24, 36, 48, 60, 72, 84, 96, 100, and 104, for subjects who were responders at PA0008 Week 12.

Absolute and change from PA0008 Baseline for all continuous efficacy variables will be summarized descriptively by visit, by treatment group at completion of PA0008, and overall.

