### 8.1.8 American College of Rheumatology Response Criteria

ACR20 response is defined as at least a 20% improvement (decrease) from PA0008 Baseline values for each of the following:

- TJC (based on 78 joints).
- SJC (based on 76 joints).
- At least 3 of the 5 remaining core set measures:
  - Disease activity as assessed by PGADA.
  - Disease activity as assessed by PhGADA.
  - Pain as assessed by PtAAP.
  - Physical function as assessed by the HAQ-DI.
  - Acute phase response as assessed by the CRP.

ACR response will be assessed using component assessments from the same analysis visit, ie, after applying any visit mapping as outlined in Section 3.5.

The following rules will be applied:

- For component scores with a Baseline value of 0, the percentage improvement is not calculable and will be considered as not having met the criteria for improvement at each visit. This will be applied and considered to be part of the OC analysis.
- In the case of partial data at a specific visit, if there are sufficient data to calculate a response eg, if results are available for TJC, SJC and at least 3 of the remaining core set assessments and these fulfil the criteria for percentage improvement (eg, 20% improvement for ACR20), this subject will be included in the summary of OC results as an ACR20 responder at the specific visit.
- Similarly, if there are sufficient data to calculate nonresponse regardless of missing data, this subject will be included in the summary of OC results as a nonresponder at the specific visit.
- For all non-missed visits, if it is not possible to determine response or nonresponse due to missing component scores, this subject will be excluded from the OC analysis at the specific visit, and regarded as a nonresponse in the NRI analysis.

Further details regarding these calculation algorithms and rules for handling missing components are provided in [Section 12.1](#).

ACR50 and ACR70 are defined similarly, using a 50% or 70% improvement from Baseline, respectively. An ACR70 responder at a given visit is therefore also an ACR50 and an ACR20 responder.

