If a subject has experienced an improvement, this measure will be positive. If a subject has experienced a worsening in their condition, this measure will be negative.

The PASI75, PASI90, and PASI100 responses will be 1 if there was at least 75%, 90%, and 100% (respectively) improvement from PA0008 Baseline in the PASI score, and 0 if there was less than the cut-off value. A PASI100 responder at a given visit is therefore also a PASI90 and a PASI75 responder.

If BSA affected by psoriasis (determined by the BSA palm method described in [Section 8.1.9](#)) is <3% at PA0008 Baseline (or BSA at PA0008 Baseline is missing) then the PASI response will be set to missing.

Summaries of PASI responses will be restricted to subjects with a BSA affected by psoriasis of  $\geq 3\%$  at PA0008 Baseline.

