## 12 APPENDIX

### 12.1 American College of Rheumatology Response Criteria

The rules for handling missing data in relation to defining the achievement of ACR20 response are provided in [Table 12-1](#). Similar rules will apply for the definition of ACR50 and ACR70. This table also indicates, where appropriate, the imputation as a nonresponder (DTYPE = WC) in the analysis datasets for the NRI analyses. For tables presented on OC data, the data selected will include all instances where DTYPE is not populated in the analysis datasets.

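### SAP 3.1 conflicts with SAP 8.1.8, 12.1 and 12.2 on the denominator for observed-case responder percentages; if 3.1 is followed, the OC percentage for ACR, PASI and MDA repeats the NRI percentage

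*SAP*

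**What the plan says.** **General rule.** SAP 3.1: "The denominator for percentages will be based on the number of subjects included in the respective analysis set". For OC summaries, the same section says that "subjects with missing data will be accounted for by including a" category labelled Missing as the last row. It gives no separate OC denominator.

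**NRI.** SAP 4.2.1: "For each visit, subjects with missing data or who have dropped out of the study will be counted as nonresponders".

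**Role of OC.** SAP 8: "As a sensitivity analysis, summaries will be repeated based on non-imputed (OC) data for the following variables". The list covers ACR20/50/70, PASI75/90/100, MDA, MASES and LDI. SAP Table 4-2 marks NRI as primary for ACR, PASI and MDA, with OC as secondary for all three and multiple imputation (MI) as secondary for ACR and PASI only.

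**Text pointing the other way.** SAP 8.1.8, on an ACR response that cannot be determined at a visit that took place: "this subject will be excluded from the OC analysis at the specific visit, and regarded as a nonresponse in the NRI analysis". SAP 12.1 (ACR) and, in the same words, 12.2 (MDA): "For tables presented on OC data, the data selected will include all instances where DTYPE is not populated in the analysis datasets". DTYPE is filled with WC when a nonresponse has been imputed.

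**PASI.** SAP 8.1.10: "Summaries of PASI responses will be restricted to subjects with a BSA affected by psoriasis of" 3% or more at PA0008 Baseline. That section has no OC exclusion rule like those in 8.1.8, 12.1 and 12.2.

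**Protocol 13.8**, on the observed-data analysis: "Subjects with missing data or who have prematurely finished the study will be treated as missing". It names no denominator.

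**The concern.** An OC analysis of a responder endpoint normally shows what happens when missing subjects are not scored as failures. Under the literal SAP 3.1 rule they stop being labelled failures but stay in the denominator. The responder percentage therefore does not move, and matching NRI and OC columns could be taken for robustness to missing data when the match is arithmetic.

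The second risk is inconsistency. One programmer could follow 3.1 and another 8.1.8 with 12.1 and 12.2; both would be following the SAP, and they would report different OC percentages.

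Three features of this study make the choice relevant:

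- For MDA, OC is the only sensitivity method.
- SAP 4.2.2 says PASI is known to be missing at some visits, because the schedule originally called for it only when BSA at that visit was at least 3%. NRI scores those visits as failures.
- SAP 4.2.1 names OC, with LOCF, as a possible fallback if the MI model does not run.

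**Working it through.** The documents state no figure to reproduce, so the check is algebra plus a pass through the SAP's own derivation tables.

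**Notation.** For one endpoint at one visit, N is the number of subjects in the summarised set (FAS; for PASI, FAS subjects with BSA of at least 3% at PA0008 Baseline). Of these, m have no determinable response and r are observed responders.

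**Step 1: can imputation create a responder?** Each of the 7 ACR components or 7 MDA criteria can be met, not met or missing, giving 3^7 = 2187 patterns. Running all of them through SAP Tables 12-1 and 12-2 gives:

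| Result | ACR | MDA |
|---|---|---|
| Y, DTYPE blank | 51 | 99 |
| Y, DTYPE = WC | 0 | 0 |
| N, DTYPE = WC | 717 | 1149 |
| N, DTYPE blank | 1419 | 939 |
| Total | 2187 | 2187 |

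The Y counts can be checked by hand. ACR needs both joint counts improved and at least 3 of 5 others: 10×4 + 5×2 + 1 = 51. MDA needs at least 5 of 7: 21×4 + 7×2 + 1 = 99. Every imputed record is an N. For PASI, NRI likewise only assigns nonresponse. So r is the same under NRI and OC, subject to Step 4.

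**Step 2: the percentages.**

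- NRI = r/N.
- OC under SAP 3.1 = r/N, with m shown in the Missing row.
- OC on determinable responses = r/(N−m).

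The first two are identical for every m. Only the split between nonresponder and missing changes.

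**Step 3: size of the difference between the two OC readings.** Let p = r/(N−m) be the observed response rate and f = m/N the missing fraction. Then r/N = p(1−f), and the gap is p − p(1−f) = p×f. The documents give neither p nor f, so both are assumed. N = 200 is the enrolment ceiling in SAP 2.4; apart from rounding, the gap does not depend on it.

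| Missing | p = 40%: NRI and OC(3.1) → OC on determinable | p = 80%: NRI and OC(3.1) → OC on determinable | Gap (points) |
|---|---|---|---|
| 5% (m = 10) | 38.0 → 40.0 | 76.0 → 80.0 | 2.0 to 4.0 |
| 10% (m = 20) | 36.0 → 40.0 | 72.0 → 80.0 | 4.0 to 8.0 |
| 20% (m = 40) | 32.0 → 40.0 | 64.0 → 80.0 | 8.0 to 16.0 |
| 30% (m = 60) | 28.0 → 40.0 | 56.0 → 80.0 | 12.0 to 24.0 |

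Mid-range case: m = 40 and p = 60% give r = 160×0.60 = 96. NRI = 96/200 = 48.0%, OC under 3.1 = 48.0%, and OC on determinable responses = 96/160 = 60.0%.

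**Step 4: the exception.** SAP 3.5 maps Early Termination assessments to a scheduled visit and includes them in that visit's summary. If the NRI sentence in 4.2.1 is read as failing every dropout even where such a mapped assessment is a response, that subject counts under OC and not under NRI. OC under 3.1 would then exceed NRI by the number of such subjects divided by N.

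**Step 5: do the other sections settle the denominator?** SAP 8.1.8 alone covers only visits that took place. Tables 12-1 and 12-2 reach further: a missed visit has no components, falls in a WC row, and is dropped from OC by the selection rule. For ACR and MDA these sections therefore point to r/(N−m). None of them says so, none overrides the explicit rule in 3.1, and none applies to PASI.

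**The case against.** The best defence is that 3.1 is a general presentation rule and the endpoint sections are more specific. Read with 12.1 and 12.2, OC tables contain only non-imputed records, which naturally gives r/(N−m) for ACR and MDA, including missed visits. The SAP narrows the analysis set elsewhere too: PASI, MASES and LDI summaries are restricted to Baseline subsets. This stands as evidence of probable intent. It does not remove the conflict, because selecting records is not stating a denominator, and 3.1 addresses OC summaries expressly.

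A reader might infer that the OC analysis is bound to duplicate NRI and tests nothing. The documents do not support that, for three reasons:

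- The SAP is in conflict with itself on this point, not settled on r/N.
- Even under 3.1 the Missing row is printed, so r/(N−m) takes one division and nothing is concealed.
- OC does not stand alone for ACR or PASI. ACR also has the MI analysis (SAP 4.2.1). PASI has MI and the two BSA-based supplementary analyses in SAP 4.2.2.

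Nor do the documents show that dropouts and missed visits make up most of the missing data. For PASI they name a different cause, the schedule error.

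It is also fair to say that little hangs on the number. The study is a single-arm safety extension with no primary efficacy variable (SAP 2.2.2.1) and no decision rule on an OC percentage. MDA is an other variable, not a secondary one. This lowers the severity but does not justify leaving two incompatible rules in the plan.

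**Conclusion.** The point holds as a conflict with a definite consequence. SAP 3.1 is the only explicit denominator rule; if it is applied, OC and NRI responder percentages coincide for ACR, PASI and MDA at any level of missingness, apart from the mapped Early Termination case. If the reading suggested by 8.1.8, 12.1 and 12.2 is applied, they differ by p×f. The identity rests on the SAP's own tables. The 2 to 24 points is illustrative only and rests on the assumed response and missing rates.

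The consequence is greatest for MDA, and smaller for ACR and PASI because of their other analyses. MASES and LDI are continuous and unaffected. Severity: should-fix, since the endpoints concerned are descriptive and secondary or other.

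**What to change.** State in SAP 3.1, and repeat in 8.2 and 8.3, that for OC summaries of ACR20/50/70, PASI75/90/100 and MDA the percentage is responders divided by subjects with a determinable response at that visit, displayed as n/Nsub, with the number missing given as a count without a percentage.

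Align 8.1.8, 12.1 and 12.2 with that sentence so that one rule covers partial components, missed visits and dropouts, and add the same rule for PASI in 8.1.10. While doing so, say in 4.2.1 whether a dropout with a mapped Early Termination response counts as a responder under NRI at that visit.

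The cost is a few sentences of SAP text and a changed denominator in tables already planned. No new data or analyses are needed. Where responses are missing and there are observed responders, the OC percentages will then differ from the NRI percentages.

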**Table 3-1: Decimal places for derived efficacy variables**

Variable	Decimal places used for minimum and maximum	Decimal places used for mean, SD and median
MASES	1	2
LDI	0	1
SJC, TJC	0	1
DAS28(CRP)	2	3
PsAID-9	2	3
SF-36 MCS	2	3
SF-36 PCS	2	3
HADS-A	0	1
HADS-D	0	1
HAQ-DI	2	3

DAS28(CRP)=Disease Activity Score 28 joint count C-reactive protein; HADS-A=Hospital Anxiety and Depression Scale – Anxiety; HADS-D=Hospital Anxiety and Depression Scale – Depression; HAQ-DI=Health Assessment Questionnaire - Disability Index; LDI=Leeds Dactylitis Index; MASES=Maastricht Ankylosing Spondylitis Enthesitis Index; PsAID-9=Psoriatic Arthritis Impact of Disease-9; SD=standard deviation; SF-36 MCS=Short Form 36-Item – Mental Component Summary; SF-36 PCS=Short Form 36-Item – Physical Component Summary; SJC=swollen joint count; TJC=tender joint count.

The abbreviation **BKZ** will be used for bimekizumab in table and listings headers.

All data will be presented in by-subject data listings sorted by planned (randomized) treatment group at completion of PA0008 (for efficacy listings) or actual treatment group at completion of PA0008 (for all other listings), site, subject number, variable (where applicable), and visit (where applicable). All listings will include scheduled, repeated and unscheduled measurements in chronological order. Dates will be presented in the format ‘YYYY-MM-DD’ and times will be presented in 24-hour clock format as ‘hh:mm’.

In all listings (where applicable) the subject level demographic information (ie, gender, age, race, weight) will be based on the data reported at PA0008 Baseline.

## 3.2 General study level definitions

### 3.2.1 Relative day

Two relative days will be calculated, these will be relative to the following *reference dates*; the first relative to the start date of study medication (placebo or bimekizumab) in PA0008 and the second relative to the start date of study medication in PA0009. Relative day will be calculated as:

$$\text{Current date} - \text{reference date} + 1 \quad (1)$$

for dates on or after the reference date, and:

$$\text{Current date} - \text{reference date} \quad (2)$$

for dates before the reference date.

Additional character relative day variables will be derived for inclusion in listings:

$$\text{Current date} - \text{reference date} + 1 \quad (3)$$

for dates on or after the reference date and on or before the end date of study medication (no prefix),

$$\text{Current date} - \text{reference date} \quad (4)$$

for dates before the reference date ('-' prefix), and:

$$\text{Current date} - \text{end date of study medication in PA0009} \quad (5)$$

for dates after the end date of study medication (with '+' prefix).

Relative day will not be calculated if dates are partial or missing.

### 3.2.2 Study periods

The following study periods are defined:

- **Treatment Period:** The Treatment Period (100 weeks) starts at the start date of study medication in PA0009 and ends at the end date of study medication.
- **Dosing period:** The dosing period starts at the start date of study medication in PA0009 and ends at 1 dosing interval (28 days) after the end date of study medication.
- **SFU Period:** The SFU Period starts on the day after the end date of study medication and ends at the SFU visit scheduled for 20 weeks after the end date of study medication.

### 3.3 Definition of Baseline values

The Baseline value defined in the PA0008 database will be used as a Baseline for PA0009, without additional derivation. The change from PA0008 Baseline will be calculated.

Due to a change in laboratory vendor between PA0008 and PA0009, laboratory values (with the exception of CRP) will use the PA0009 Laboratory Baseline, defined as the earliest post-EV value recorded in PA0009 at or prior to PA0009 Week 12). Change from PA0009 Laboratory Baseline will be calculated for these parameters.

The CRP values from the 2 analyzing laboratories have been calibrated, so change from PA0008 Baseline will be calculated for CRP.

